1.0 INTRODUCTION AND BACKGROUND

1.1 Common and Flat Warts of Hand and Fingers

Non-genital warts (*verruca vulgaris*) are an extremely common, benign, and usually a self-limited skin disease. Infection of epidermal cells with the human papillomavirus (HPV) results in cell proliferation and a thickened, round, raised papule on the skin ranging in size from a pinhead to 10 mm. The appearance of warts is determined by the type of virus and the location of the infection. There are several reasons why some individuals are affected by warts, and others remain trouble free. These include: the type and strength of the viral strain, the health of the exposed person, and the strength of an individual's immune response. Any area of skin can be infected, but the most common sites are the hands and feet. **Common warts** are most often seen on the hands and present as skin-colored papules with a rough 'verrucous' surface. **Flat warts** are most often seen on the backs of the hands and on the legs. They appear as slightly elevated, small plaques that are skin-colored or light brown. **Plantar warts** occur on the soles of the feet and look like very thick callouses.

Current Care

Current treatments for common and flat warts involve destruction of the infected cells either chemically or physically and treatment depends on the size, location, number, type, age of the patient, risk of scarring and patients' commitment to the therapy. The clinical management of these warts is challenging, and no current treatment is singularly effective, especially against warts that are recalcitrant. These include non-surgical, pharmacologic and surgical treatment modalities: topical peeling methods like salicylic acid; immune modulators using contact immunotherapies; intralesional candida antigen or bleomycin and; cryotherapy; duct tape occlusion; photodynamic treatment; pulsed dye laser; and general surgical procedures.

1.2 Non-Surgical Approach

Chemical Destruction:

Salicylic Acid

The use of salicylic acid is one of the two most commonly used treatments for warts. Dermatologists prescribe chemical destruction treatments where patients apply an over-the-counter preparation, usually less than 17% salicylic acid or prescription salicylic acid containing up to 70% salicylic acid at home every day. Treatment response rates of 40-84% with an average of 61% have been reported as an effective therapy for non-genital cutaneous warts.¹ Minor skin irritation was reported occasionally in some of the other trials, but generally there were no major harmful effects of topical salicylic acid.² A systematic review of local treatments of cutaneous warts by Mitsuishi et al., found evidence that topical treatments with salicylic acid have a therapeutic effect, with a cure rate of 75 percent compared with 34-48 percent in placebo controls.^{1,3} Other agents used for chemical destruction are monochloracetic acid, dichloracetic acid, trichloroacetic acid, silver nitrate, glycolic acid and 80% phenol in solution. Complications associated with using chemicals include pain, hyperpigmentation, hypopigmentation, burning sensation and erythema.⁴

Cantharidin

Cantharidin is used as an agent in the clinic by "painting" the wart causing oxidative stress by inhibiting phosphatases 1 and 2A that damages both DNA single- and double-strand breaks and triggers p53 dependent apoptosis.⁴ Cantharidin causes a blister to form under the wart. In a week or so, the patient returns to the office and the dermatologist clips away the dead wart.

Immune Modulators

This treatment uses the patient's own immune system to fight the warts. Forms of immune modulators include imiquimod, intralesional immune modulators using Candida antigen or anti-cancer such as Bleomycin; contact immunotherapy, cimetidine, zinc, and retinoids. Because wart proliferation is controlled by the immune system, various methods have been used to stimulate the immunologic response to HPV. This treatment is used when the warts remain despite using other treatments and the ability to treat many lesions simultaneously. One type of immunotherapy involves applying a chemical diphenylcyclopropenone (DPCP). Among these are topically applied inorganic molecules capable of eliciting contact hypersensitivity, such as imiquimod and intralesional interferons⁵ to the warts. A mild allergic reaction occurs around the treated warts which stimulates the body's innate response to fight the virus.

Physical Destruction:

Cryotherapy

For common warts in adults and older children, cryotherapy is a standard treatment and can be done in the physician's office. Cryotherapy involves freezing a wart using a very cold substance (usually liquid nitrogen). The liquid nitrogen application usually takes less than a minute and most warts require 1 to 4 treatments, with 1 to 3 weeks between each treatment. Pain from cryotherapy can last up to 3 days. Healing is generally quick (7 to 14 days) with little or no scarring⁶. It can cause dark spots in people who have dark skin. With cryotherapy, it is common for repeat treatments.

Laser

Laser treatment is an option, mainly for warts that have not responded to other therapies. Before laser treatment, the dermatologist may numb the wart with an anesthetic injection.

1.3 Surgical Approach

Electrosurgery and Curettage:

Electrosurgery (burning) is an available treatment for common warts, filiform warts, and foot warts. Curettage involves scraping off (curetting) the wart with a sharp knife or small, spoon-shaped tool. These two procedures often are used together. The dermatologist may remove the wart by scraping it off before or after electrosurgery.

Excision:

The wart may cut off or surgically excised in combination to using other applications previously mentioned.

1.4 Nano-Pulse Stimulation (NPS) Therapy:

The NPS medical device is intended to clear the skin of benign, undesired skin lesions as an alternative to surgery and other more destructive methods for removing benign lesions. The system is designed to deliver a timed series of very low energy, high amplitude (about the same as the voltage of static electricity) pulses of a time length between 100 and 750 nanoseconds (billions of a second). The non-thermal effect on tissue takes place in a very shallow depth of skin directly below the sterile treatment tip. The device emits significantly less thermal energy than existing laser, electro-surgery or electro-cautery equipment.

Extensive in vitro research demonstrates stimulation of a form of delayed programmed cell death in a treated area, which is one of the identified mechanisms for observations of clinical and histologic changes to cells in multiple studies of in-vivo treated tissue in both humans and animals. In pre-clinical studies with over 1000 rats and mice, nano-pulsed devices have been demonstrated to reduce or eliminate malignant tumors with a clinically acceptable margin of safety. A pilot clinical trial of common skin cancer lesions was conducted under IRB oversight in 2012 with a similar version of the NPS device, with the findings published in Experimental Dermatology. A total of ten basal cell carcinoma lesions on the skin of three subjects were treated with a range of settings. Seven of the ten lesions were free of basal cells at the conclusion of the study, two partially resolved, and one recurred. No scars were visible at the healed sites of any of the successfully treated lesions. In another pre-clinical study, NPS treatment was applied to a human papillomavirus type 16 (HPV 16)-transformed C3.43 mouse tumor cell model in 15 immuno-competent mice. The results showed that NPS technology is effective in eliminating primary tumors through the induction of immunogenic cell death while subsequently increasing the number of tumor-infiltrating lymphocytes within the tumor microenvironment. The mice were re-challenged and about half of the mice that had cleared established tumors were protected against tumor re-challenge on the opposite flank, indicating that NPS technology has an immune effect that prevents successful tumor re-challenge.⁷

Prior NPS Therapy Clinical Studies:

The NPS device has been successfully deployed in several clinical studies of skin and subcutaneous structures. As of the date of this writing, the following studies have been successfully conducted and concluded: 1) A histological study evaluating use of the device on healthy abdominal human tissue in a dose-response study; 2) A histological study evaluating use of the NPS therapy and comparative devices on healthy abdominal human tissue, 3) histological study following use of the therapy on healthy facial skin tissue in the pre-auricular area; 4) A multi-center study in the treatment of Seborrheic Keratosis lesions. Additional detailed summaries of these studies follows.

Abdominal Tissue (Pre-Abdominoplasty) Studies

Study Name: Nano-Pulse Human Tissue Study

A total of 8 subjects participated in this prospective, single site, non-randomized study. All subjects were females representing a wide range of Fitzpatrick Skin Tone Classifications, and ranging in age from the low 40's to middle 60's.

The study was comprised of two sequential segments. The first segment evaluated the serialized use of the test device in demarcated locations on intact abdominal skin predetermined for subsequent resection during a standard abdominoplasty scheduled later. The primary endpoint of the first segment of the study was to establish that the trauma to the

tested skin would be minimal over a range of six progressively increasing energy levels. The appearance of each intact tested tissue location was comparable to that anticipated following any minor surgical excisional procedure. A total of 210 NPS applications were tested and analyzed in this study.

Lidocaine was injected prior to use of the NPS skin exposure. Subjects reported little or no sensation during the treatment session. Subjects further reported little or no discomfort after the Lidocaine effect had diminished. There were no adverse events, no reports of bleeding, and no scarring noted by the Investigator at the end of the 60-day study

The second segment of the study called for the histological analysis of tissue samples prepared from the abdominal section that were resected at the time of the abdominoplasty. Internal technicians and outside expert dermatopathologists evaluated the skin samples using standardized methods of microscopic analysis. This second segment did not impact the participating subject as it occurred after the abdominoplasty procedure. Consequently, Pulse Biosciences, Inc. secured IRB oversight concentrated on the first segment of the study. It should be noted however that the histological analysis to date confirmed that the NPS was successful in achieving its intended effect across the range of tested energy settings.

Abdominal Tissue (Pre-Abdominoplasty) Comparative Studies

Study Name: Nano-Pulse Human Tissue Study

A total of 2 subjects participated in this prospective, single site, non-randomized study. Both subjects were females representing two different Fitzpatrick Skin Tone Classifications and ranging from the high 20's to low 40's in age.

The primary purpose of the study was to collect tissue samples from healthy human resected tissue that had been exposed to various methods of partial tissue ablation prior to a planned abdominoplasty resection date. The skin samples were taken from a section of abdominal skin that was previously exposed to the effect of the NPS therapy during the same time period as two comparator medical devices considered to be the "gold standards" for tissue ablation. Histological analysis of the resected abdominoplasty tissue was performed on samples taken from sites treated with the 2 "gold standard" devices as well as the NPS therapy.

The study is best described as comprised of two sequential segments. The first segment called for the serialized use of the NPS test device and the gold standard "comparatives" in specific locations on intact abdominal skin predetermined to be resected during a standard abdominoplasty. The impact of the study test device, the comparative devices and/or the study process ceased at the time of the abdominoplasty. The primary endpoint of the first segment of the study was to establish that the apparent trauma to the tested skin was minimal for all devices. The appearance of each intact tissue location that was tested with the NPS therapy or the two comparative systems was comparable to that anticipated following any minor surgical excision procedure.

Lidocaine was injected prior to use of the NPS skin exposure, and one of the comparators. Subjects reported little or no sensation during the multiple treatment sessions. Subjects further reported little or no discomfort after the Lidocaine effect had diminished in the days following each treatment. There were no adverse events, no reports of bleeding, and no scarring in the NPS therapy group noted by the Investigator at the end of the 60-day study

The second segment of the study called for the histological analysis of tissue samples prepared

from the abdominal section that was resected at the time of the abdominoplasty. Internal technicians and outside expert dermatopathologists evaluated the skin samples using standardized methods of microscopic analysis.

Pre-Auricular Tissue (Pre-Face Lift) Studies

Study Name: Nano-Pulse Pre-Auricular Tissue Study

A total of 3 subjects participated in this prospective, single site, non-randomized study. Two of the subjects were females and one was a male representing different Fitzpatrick Skin Tone Classifications and all were over the age of 50 years of age.

The study was comprised of two sequential segments. The first segment called for the serialized use of the test device in several locations on intact facial skin pre-determined to be resected during a standard face-lift, which is typically a small section in front of the ear (the pre-auricular area).

The primary endpoint of the first segment of the study was to establish that the visually apparent trauma to the tested skin would be minimal and the appearance of each intact tested tissue location was comparable to the appearance that is anticipated following any minor surgical procedure.

Lidocaine was injected prior to NPS therapy administration to the skin surface. After the first NPS exposure, subjects returned at varying time intervals prior to their scheduled face lift procedure for additional NPS administrations on demarcated areas on each side of their face using varying tip sizes and energy settings. Subjects reported little or no sensation during the NPS administrations. Subjects further reported little or no discomfort after the local anesthetic effect had diminished. There were no adverse events, no reports of bleeding and no scarring noted by the Investigator at the end of the study.

Following the same model as described above, additional studies were performed involving pre-auricular tissue of facial skin in 3 subjects scheduled for eventual face lift procedures. The sole Investigator for this series (NP-PT-003) was [name], MD., Plastic Surgeon, in San Mateo, CA. As noted above for the Pre-Abdominoplasty study, local anesthetic was administered prior to the NPS skin exposure. Subjects reported little or no sensation during the treatment session. Subjects further reported little or no discomfort after the local anesthetic effect had diminished. There were no adverse events, no reports of bleeding, and no scarring noted by the PI at the end of the 60-day study.

Warts Feasibility Study (NP-WF-007)

Study Name: Nano-Pulse Non-genital Warts Feasibility Study

Nineteen (19) treated adult subjects were required to have 2-5 non-genital, off-face cutaneous warts in this multi-center feasibility study. Up to four warts were designated to be treated, while one wart was designated as the sham control. Subjects received an initial NPS-treatment and returned for 3 to 5 follow-up evaluations at 7 days, 30 days, 60 days, 90 days and 120 days after the initial treatment. Each wart was evaluated for size reduction and the condition of the skin. If the reduction in wart size met study criteria, the wart was eligible for an additional treatment and at the discretion of the investigator.

Six (6) of the 19 subjects were male and 13 were female. Ages ranged from 23 to 71, with an average age of 48. Subjects had Fitzpatrick skin types ranging from I to III. A total of 58 warts have been included in the study at the time of this report. 34 warts were identified for treatment and 19 warts as controls. 70% of the study warts had been previously treated with another modality and were not successful at eliminating the wart. 69% of treated warts were located on the hand/fingers and the remaining 31% of treated were located on the feet. Twenty-five (25%) of treated warts received a single treatment, and 75% received two treatments. Of the treated warts, 50% showed 100% reduction in size, 21% showed a 50-90% reduction in size, and 26% showed less than a 50% reduction in size at the last reported visit. Twenty-nine (29%) of the treated warts showed 100% reduction after a single treatment. There were two instances where the control wart showed 100% reduction in size, suggesting that there may be an immune response. Preliminary data analysis indicates that complete coverage of the wart within the treatment zone is required. There is also a trend toward the use of higher settings within the allotted range for better outcomes. There were no instances of hypopigmentation noted, and 3 cases of mild hyperpigmentation at 60 days.

The high rate of wart size reduction suggests the utility of the unique NPS cellular mechanism for the treatment of non-genital, cutaneous warts. Based on these initial results, a larger pivotal study is warranted and will be conducted in the future to further evaluate the use of NPS technology for the treatment of warts.

2.0 STUDY DEVICE DESCRIPTION

2.1 Pulse Bioscience CellFX™ System

The Pulse Bioscience CellFX™ System uses a proprietary platform technology called Nano-Pulse Stimulation™ (NPS™). NPS technology utilizes nanosecond (billionth of a second) pulses of energy that penetrate into the cytoplasm and organelles to induce regulated cell death in a target lesion. The pulses are applied directly to targeted tissue using small microneedles.

The CellFX System is intended for the reduction and/or removal of benign and non-benign lesions.

The CellFX System consists of:

- CellFX Console - The Console consists of all the electronics and controls required to generate a nanosecond pulsed electric field. A touchscreen provides the user interface to the system. The power cord electrically connects the Console to the AC mains outlet.
- CellFX Handpiece (re-usable) - When attached to a Single Patient Use Retractable Tip (Treatment Tip), the Handpiece is held by the user to deliver a timed series of energy pulses (referred to as a "Cycle") from the CellFX Console. The Handpiece has a custom receptacle for attachment to the Treatment Tip, a custom connector that plugs into the Console with a 10-foot cable, a hook for hanging the Handpiece on the Console, a Finger Switch for cycle activation, a LED status indicator, and a pair of side buttons on each side of the Handpiece.
- CellFX Single Patient Use Retractable Tips – A sterile Single Patient Use Tip attaches to the Handpiece. The Tip holds two to three arrays of needles that define the intended treatment area (i.e. lesion zone) where the pulsed electric field is applied. There are fiducial markers on each side of the retractable tip portion, one marker on each side perpendicular to the row of needles and second on each side parallel with the rows of needles that can be used to align to the treatment area.

3.0 PROTOCOL

3.1 Study Purpose and Objectives

The purpose of this study is to evaluate the safety and effectiveness of the CellFX System in patients with cutaneous non-genital warts on all areas of the body, excluding the face.

The study objectives are listed below:

- Evaluate the condition of skin in the treatment areas (erythema, etc.) over the course of 7 to 120 days post-initial NPS treatment
- Evaluate the overall response to NPS treatment by:
 1. Wart clearance (generally accepted as complete clearance of warts from the treated area)
 2. Wart reduction (reduction in the total number of warts)
- Evaluate and assess adverse effects of treatment

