3.2 Study Design Overview

The study is designed as a prospective, non-randomized, multicenter pivotal study to evaluate the safety and effectiveness of the CellFX System in patients with non-genital warts, excluding the face. Macrophotography of all treated warts will be captured along with Investigator assessments using a wart measurement scale and tissue response. One of the warts for each subject will be untreated and will serve as the subject's internal control. Please note the Investigator has the option at baseline and at each follow-up visit for curettage of the targeted site prior to NPS treatment. Additionally, at the 30-day, 60-day and 90-day visits the Investigator has the option to retreat any previously treated lesion.

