3.4. Clinical Study Duration

It is anticipated that the enrollment of subjects in this pivotal study will take approximately 4-months. All subjects included in this clinical investigation will return for follow-up visits at 7, 30, 60, 90 and 120-days post-initial NPS treatment. All lesions will have the possibility of being retreated up to 3 times, with a maximum of 4 total NPS treatments over the course of the study. Total study duration is approximately 8 months.

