4.3 Study Visits

4.3.1 Screening/Baseline Procedures including NPS Treatment – Visit 1 (Day 0)

The following evaluations and procedures are required at the time of subject screening/baseline

- Signed Informed Consent
- Dermatologic Medical History/Demographics
- Wart classification and anatomic location for all study lesions
- Inclusion and Exclusion criteria

Activities on 1st Study Visit Day - NPS Treatment Day

The following assessments and procedures will be performed

- Using a randomization method, the selected wart(s) will be designated to be treated and one will be designated as an untreated control.
- Each selected lesion will be numerically labeled, and photographic images will be taken before the local anesthetic/numbing.
- Local anesthetic/numbing will be administered to all study lesions.
- NPS treatment #1 will be delivered to all lesions.

- Subject will rate the level of pain from a specified pain score.
- Photographic images of all lesions will be taken immediately post-NPS treatment.
- A light bandage and any PI recommended dressing may be applied.
- Adverse event assessment will be performed.

4.3.2 7-Day Follow-up – Visit 2

The following assessments and procedures will be performed

- Photographic images of all study lesions will be taken.
- Each lesion will be clinically assessed, and the appearance will be rated according to specified criteria.
- Adverse event assessment will be performed.

4.3.3 30-Day Follow-Up / Possible NPS Re-Treatment - Visit 3

The following assessments and procedures will be performed

- Photographic images of all study lesions will be taken.
- Wart reduction assessment, including measurement will be performed.
- All lesions will be clinically assessed, and the appearance will be rated according specific criteria.
- All lesions that are rated other than “Clear” are eligible to receive a retreatment with NPS of those lesions.
- In case of an NPS retreatment:
 - Images of each of the selected lesions will be taken before local anesthetic/numbing and after the NPS treatment.
 - Local anesthesia/numbing will be applied to the identified lesions.
 - NPS treatment will be delivered.
 - Subject will rate the level of pain from a specified pain score.
 - A light bandage and any PI recommended dressing may be applied.
- Adverse event assessment will be performed.

4.3.4 60-Day Follow-Up / Possible NPS Re-Treatment - Visit 4

The following assessments and procedures will be performed

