- Photographic images of all study lesions will be taken.
- Wart reduction assessment, including measurement will be performed.
- All lesions will be clinically assessed, and the appearance will be rated according specific criteria.
- All lesions that are rated other than “Clear” are eligible to receive an NPS retreatment of those lesions.
- In case of an NPS retreatment:

- Images of each of the selected lesions will be taken before local anesthesia/numbing and after the NPS treatment.
- Local anesthesia/numbing will be applied to the identified lesions.
- NPS treatment will be delivered.
- Subject will rate the level of pain from a specified pain score.
- A light bandage and any PI recommended dressing may be applied.

- Adverse event assessment will be performed.

4.3.5 90-Day Follow-Up / Possible NPS Re-Treatment- Visit 5

The following assessments and procedures will be performed

- Photographic images of all study lesions will be taken.
- Wart reduction assessment, including measurement will be performed.
- All lesions will be clinically assessed, and the appearance will be rated according specific criteria.
- All lesions that are rated other than “Clear” are eligible to receive an NPS retreatment of those lesions.

- In case of an NPS retreatment:
 - Images of each of the selected lesions will be taken before local anesthetic/numbing and after the NPS treatment.
 - Local anesthesia/numbing will be applied to the identified lesions.
 - NPS treatment will be delivered.
 - Subject will rate the level of pain from a specified pain score.
 - A light bandage and any PI recommended dressing may be applied.

- Adverse event assessment will be performed.

4.3.6 120-Day Follow-Up – Visit 6 (Final Study Visit)

The following assessments and procedures will be performed

- Photographic images of all study lesions will be taken.
- Wart reduction assessment, including measurement will be performed.
- All lesions will be clinically assessed, and the appearance will be rated according specific criteria.
- Adverse event assessment will be performed.
- Subject satisfaction will be evaluated for the appearance of the treated lesions.

Table 2 lists assessments and procedures required at each study visit.

Table 2 : Schedule of Events and Evaluations

Study Visit Interval	#1 0-days Enrollment NPS TX #1	#2 7-days Post-NPS TX #1	#3 30-days Post-NPS TX #1	#4 60-days Post-NPS TX #1	#5 90-days Post-NPS TX #1	#6 120-days Post-NPS TX#1 (Final Visit)

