Study Visit Description	Informed Consent All eligibility criteria met TX #1 Photographic images	Lesion(s) evaluation Photographic images	Lesion(s) evaluation TX #2 (if applicable) Photographic images	Lesion(s) evaluation TX #3 (if applicable) Photographic images	Lesion(s) evaluation TX#4 (if applicable) Photographic images	Lesion(s) evaluation Subject Satisfaction Photographic images
Visit Range (# of Days Post-NPS TX #1)		5-9 days	27-37 days	57-67 days	87-97 days	120-130 days

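### Does timing the skin ratings only from the initial NPS treatment spoil the skin-condition objective when lesions can be retreated at Visits 3 to 5?

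*Protocol*

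**What the plan says.** The skin-condition objective in Protocol section 3.1 reads "Evaluate the condition of skin in the treatment areas (erythema, etc.) over the course of 7 to 120 days post-initial NPS treatment". Section 3.4 uses the same starting point for the schedule: subjects "will return for follow-up visits at 7, 30, 60, 90 and 120-days post-initial NPS treatment". The row of windows in Table 2 is likewise labelled "Visit Range (# of Days Post-NPS TX #1".

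Retreatment is part of the design. Section 3.4 states "All lesions will have the possibility of being retreated up to 3 times", with four treatments as the ceiling. Section 3.2 says that at the 30-, 60- and 90-day visits "the Investigator has the option to retreat any previously treated lesion". Sections 4.3.3 to 4.3.5 put it more narrowly: lesions not rated Clear "are eligible to receive a retreatment with NPS of those lesions" at Visit 3 and "are eligible to receive an NPS retreatment of those lesions" at Visits 4 and 5.

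At each of those three visits the list of procedures gives the skin rating ("All lesions will be clinically assessed, and the appearance will be rated according specific criteria") before any retreatment. No section counts time from the most recent treatment.

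**The concern.** Through Visit 3 every treated lesion has had one exposure when it is rated, so days since the first treatment and days since the last treatment are the same. From Visit 4 on they separate for any retreated lesion. A skin change seen at Visit 6 in a lesion last treated at Visit 5 would fall under the 120-day visit, although the exposure was about a month old. It would sit beside changes seen four months after a single treatment.

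How long a skin change lasts after exposure is central to judging it, and skin condition is the first objective listed. The mixing is also not random. Under sections 4.3.3 to 4.3.5 the recently exposed lesions are those that had not cleared, so recency of exposure goes with poor response. If Visit 4 to 6 results were shown by visit alone, with no retreatment information, a reader could not tell a lasting change from a recent one.

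**Working it through.** **Inputs.** Table 2 gives these windows, in days after treatment #1: Visit 2, 5-9; Visit 3, 27-37; Visit 4, 57-67; Visit 5, 87-97; Visit 6, 120-130. Retreatment is possible at Visits 3, 4 and 5 (sections 3.2 and 4.3.3 to 4.3.5).

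**Step 1: time since last treatment.** The shortest gap is the earliest day of the rating visit minus the latest day of the last treatment visit. The longest gap is the latest day of the rating visit minus the earliest day of the last treatment visit.

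| Rated at | Last treated at Visit 1 | At Visit 3 | At Visit 4 | At Visit 5 |
|---|---|---|---|---|
| Visit 2 | 5-9 | | | |
| Visit 3 | 27-37 | | | |
| Visit 4 | 57-67 | 57-37 = 20 to 67-27 = 40 | | |
| Visit 5 | 87-97 | 87-37 = 50 to 97-27 = 70 | 87-67 = 20 to 97-57 = 40 | |
| Visit 6 | 120-130 | 120-37 = 83 to 130-27 = 103 | 120-67 = 53 to 130-57 = 73 | 120-97 = 23 to 130-87 = 43 |

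On nominal days the gap is 30 or 60 days at Visit 4; 30, 60 or 90 at Visit 5; and 30, 60, 90 or 120 at Visit 6. Only Visit 6 spans the full one to four months. The next scheduled rating after any retreatment comes 20 to 43 days later, against 5 to 9 days after treatment #1.

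Section 3.2 allows retreatment of any previously treated lesion, while sections 4.3.3 to 4.3.5 limit it to lesions not rated Clear. Those passages need reconciling in their own right, but the day counts are the same under either.

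**Step 2: does the protocol fix a reporting rule?** Section 3.1 gives a period of observation. Section 3.4 and Table 2 give visit dates and windows. Sections 4.3.3 to 4.3.6 say what is rated at each visit. None says how the ratings will be grouped, labelled or summarised. The three places agree in counting from treatment #1, so there is no contradiction.

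**Step 3: is information lost?** Table 2 ties retreatments to Visits 3, 4 and 5, so the date of such a visit is the date of the treatment. Section 7.8 has the case report forms record procedural and follow-up data. Section 5.0 records onset and resolution dates for adverse events related to the device or procedure. Days since last treatment is therefore a subtraction of visit dates.

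**Step 4: what would a prescribed split add?** At Visit 6 there are four bands by last treatment visit. Combining last treatment visit with number of treatments gives seven groups: Visit 1 with one treatment; Visit 3 with two; Visit 4 with two or three; Visit 5 with two, three or four. Section 3.3 plans about 60 subjects. Assuming one treated wart each and an even split, that is 60/4 = 15 lesions per band or 60/7 = 8.6 per group. The groups are formed by earlier response, so they support description only.

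**The case for a change.** The strongest case for a change is that the starting point is written into an objective and not merely left open, and that retreatment may be common. In the feasibility study described in section 1.4, 75% of treated warts had two treatments. If that share recurred, which is an assumption (the percentages in that summary do not all reconcile), about three quarters of treated lesions would have a last exposure later than treatment #1 by Visit 6. The same summary reports three instances of mild hyperpigmentation at 60 days without saying how long after the last treatment they were seen, so the ambiguity has a precedent. A sentence in section 3.1 would cost little.

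Part of this stands. The gaps in time since exposure are real. A Visit 6 table of skin ratings with no retreatment information would be hard to read, and an analyst should expect to show the split.

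It does not make the protocol wrong. The harm arises only if results are reported by visit alone, and no section says they will be. Nothing in section 3.1 prevents a second time scale. Two of the difficulties would also survive the added sentence. A reaction present before a retreatment and again at the next visit cannot be classed as persistent or recent on either scale. The absence of a rating 5 to 9 days after a retreatment comes from the visit schedule.

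**Conclusion.** No change is needed. The arithmetic holds: time since last exposure varies nominally over one to two months at Visit 4, one to three at Visit 5 and one to four at Visit 6. What is absent is a table specification, not a correct rule. As written, the plan yields a true description of skin at fixed times after starting a course of up to four treatments. Describing skin by time since the last treatment answers a different, complementary question that the scheduled visits already allow.

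This rests on two assumptions: that each lesion's treatments are recorded by visit, as Table 2 and section 7.8 imply, and that the layout of the skin tables is left to a statistical analysis plan, which is not at hand. The share of lesions that will be retreated is not given, so the number affected cannot be stated. No sample size, hypothesis or decision in the protocol depends on the point, and the primary effectiveness evaluation in section 3.6.1 is unaffected.
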